#### **A. Goals and Aims**

The goal of the Aides in Respiration (AIR) study was to evaluate the effectiveness of a health coach model for improving outcomes for low-income urban patients with COPD. We conducted a randomized trial comparing 9 months of health coaching plus usual care (health coached arm) to usual care (usual care arm) alone for patients with moderate to severe COPD cared for at 7 federally qualified health centers (FQHCs). The specific aims of the study were:

Specific Aim 1. To compare disease specific quality of life for patients randomized to receive 9 months of health coaching plus usual care to those randomized to usual care alone. Our hypothesis was that mean quality of life, assessed by the Chronic Respiratory Disease Questionnaire total score and dyspnea domain score at 9 months, would be greater in patients in the health-coached arm when tested against the null hypothesis of no difference between health-coached and usual care patients.

Specific Aim 2. To compare the number of exacerbations of COPD experienced by patients in the health coached arm to those in the usual care arm during the 9 month period starting at enrollment. COPD exacerbation was defined as an emergency department visit or hospitalization for COPD-related diagnosis or the outpatient prescription of oral steroids for COPD-related diagnosis. Our hypothesis was patients in the health-coached arm would experience fewer exacerbations when tested against the null hypothesis of no difference between health-coached and usual care patients.

Specific Aim 3. To compare exercise capacity at 9 months for patients in the health-coached arm to those in the usual care arm. Our hypothesis was that patients in the health-coached arm would have greater exercises capacity as measured by the 6-minute Walk Test when tested against the null hypothesis of no difference between health-coached and usual care patients.

Specific Aim 4. To compare self-efficacy for management of their COPD for health-coached versus usual care patients at 9 months. Our hypothesis was that mean self-efficacy, as measured by Stanford Chronic Disease Self-Efficacy Scale would be greater in patients in the health coached arm when tested against the null hypothesis of no difference in self-efficacy between health-coached and usual care patients.

## **B. Study Design**

Nine-month randomized controlled parallel trial, single-blinded.

## **C. Setting**

This study was conducted at seven urban county-operated primary care clinics designated as federally qualified health centers (FQHCs) that primarily serve a low-income, publically insured patient population. Two of these sites are large academic residency teaching practices based at the public hospital that is part of the county-owned system. Pulmonary specialty care is available through the public hospital that is part of the health network. Clinic sites have integrated behavioral health services. All sites have had prior exposure to health coaching for diabetes, hypertension, and/or as part of complex care management programs.

## **D. Participants**

The study enrolled low income and vulnerable patients receiving care FQHCs because these patients experience disparities in quality of care and disease burden and have been underrepresented in clinical research studies of COPD. Multiple clinic sites were necessary to obtain an adequate sample size.

## **E. Inclusion and exclusion criteria:**

In addition to meeting diagnostic criteria for COPD, clinical inclusion for having moderate to severe COPD required at least one of the following:

- At least one hospital admission due to COPD-related diagnosis in the last 12 months;
- At least two emergency department visits due to COPD-related diagnosis in the last 12 months;
- Prescription of short term oral steroids (at least 40 mg for at least 5 days but <21 days) for respiratory symptoms in the last 12 months;
- Current prescription of anticholinergic inhaler;
- Current prescription of combination long-acting bronchodilator and corticosteroid inhaler;
- Prescription of home oxygen therapy (ever);
- Post-bronchodilator forced expiratory volume over 1 second (FEV1) < 80% of predicted (ever);
- Resting O2 Saturation  $\leq$  88% as an outpatient (ever);
- Arterial blood gas (ABG/PPO2)  $\leq$  55 mm Hg as an outpatient (ever).

Non-clinical inclusion criteria were all of the following:

- Age  $\geq$  40 years;
- Able to be reached by telephone;
- Speaking Spanish or English;

Currently a patient at one of the 7 participating clinic sites with at least 1 outpatient visit within the last 12 months and planning to continue care at clinic for the next 9 months;  
Planning to be in San Francisco area for at least 6 of the next 9 months, including at the end of study

Willing to attempt spirometry.

Exclusion criteria were any of the following:

Unable to participate in the study as judged by their PCP

Unable to travel to their primary care clinic

Unable to complete the enrollment process.

Spanish speaking patients were recruited by a bilingual research assistant. To maximize participation of from under-represented groups, we minimized exclusion criteria. Specifically, we did not exclude patients who were homeless, had substance abuse, mental illness, or other conditions as long as they were able to receive health coaching and participate in the study.

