### L. Follow-up

Participant contact information, including phone numbers, address and emails, were obtained at enrollment the best way(s) to contact the participant was established. Participants in both study arms were contacted every 3 months by the RA and asked to complete a brief interval survey (see attachments) which asked about recent exacerbations, and current smoking status. Participants were paid \$10 for each interval survey. To the extent possible, the same RA follow-up with participant each time to help build trust. For the 9-month, end of study measures, which required an in person visit, RAs met with the patient at the patients primary care clinic, helping to arrange transportation if needed. The proportion of patients completing surveys were similar between study arms at 3 and 6 months, was but higher in usual care arm at 9 months. Reasons for withdrawal from the study was documented to the extent possible, based on contacting the patient and reviewing the medical record.

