Statistical Analysis Plan
Aides in Respiration (AIR) Health Coaching for Patients with COPD

NCT02234284

Updated September 8, 2014

Uploaded March 7, 2019

Baseline participant characteristics were compared between study arms and tested for significance using chi-square for categorical variables, t-tests for normally distributed continuous variables, and appropriate non-parametric tests for non-normally distributed continuous variables. Outcomes were compared by group assignment (intention to treat) using generalized linear mixed models (GLMMs) with a normal distribution and identity link for continuous outcomes and Poisson distribution with a log link for count outcomes. GLMMs uses random effects to account for within-participant correlations, nested random effects to account for clustering, and accommodate missing data under the assumption that the outcomes are missing at random.¹⁻⁵ In all models, baseline levels of the outcome were entered as a predictor and follow-up levels as the dependent variable, with a nested random effect of practice site to account for clustering. Hypothesis tests were 2-sided with p-values<0.05 considered statistically significant. Models used available data, while sensitivity analyses were conducted repeating primary analyses with multiple imputation procedures. Additional, exploratory per protocol and sub-group analyses were also performed, limiting patients in the coached arm to those receiving at least half of the protocol target for contacts. Differential effects (effect modification) was examined for 3 pre-specified subgroups: English vs Spanish as primary language; current smokers vs other; and COPD classification GOLD category D (high symptoms and high risk) vs other.

O. References

1. Fairclough D. Design and analysis of quality of life studies in clinical trials. New York: Chapman & Hall/CRC; 2002.
2. Little RJ and Rubin DB. Statistical analysis with missing data. New York, Wiley, 1987

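### The Aim 2 exacerbation model has no time-at-risk term, and neither document says how a patient with incomplete follow-up enters the fixed 9-month count

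*Protocol*

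**What the plan says.** - **Window.** Protocol section A (Specific Aim 2) compares the number of exacerbations "during the 9 month period starting at enrollment".
- **Eligibility.** Section E requires "Planning to be in San Francisco area for at least 6 of the next 9 months, including at the end of study", so up to 3 of the 9 months may be spent elsewhere. The adjacent criterion asks that the patient be "planning to continue care at clinic for the next 9 months".
- **Model.** The SAP uses a "Poisson distribution with a log link for count outcomes". In every model, "baseline levels of the outcome were entered as a predictor and follow-up levels as the dependent variable", with a random effect for practice site. No offset, exposure or person-time term is named.
- **Missing data.** The SAP says the models "accommodate missing data under the assumption that the outcomes are missing at random". It adds: "Models used available data, while sensitivity analyses were conducted repeating primary analyses with multiple imputation procedures".
- **Ascertainment.** Table 1 gives medical record review as the source for exacerbations. Section K says the 3- and 6-month surveys asked about emergency visits and admissions outside the county hospital and that those records were requested. It also says utilization was reviewed at the end of the study from the EMR and outside records.
- **Loss.** Section M assumes 20% attrition. Section L reports similar survey completion by arm at 3 and 6 months but higher completion in usual care at 9 months, without figures. It adds: "Reasons for withdrawal from the study was documented to the extent possible, based on contacting the patient and reviewing the medical record".

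**The concern.** A count over a fixed window is comparable between patients only if all are observed for the whole window. Here some will die, withdraw or leave the county system, and the model has no term for how long each was observed. Suppose a patient dies at month 2 after one exacerbation and the chart count is used unadjusted. That patient enters exactly like one followed for 9 months with one exacerbation, although the observed rates differ by a factor of 9/2 = 4.5.

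Shorter observation then looks like benefit. The only information on balance, the lower 9-month completion in the coached arm, points towards coaching. At stake is the first-listed secondary outcome, sized for an expected reduction of 20 to 26%.

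**Working it through.** **1. The plan's own power figures.** Tables 2 and 3 give power .90 (100 per arm) and .81 (76 per arm) for a 22% reduction. No control-arm rate or dispersion is given, so neither figure can be derived directly. They can be checked against each other. With control rate μ per 9 months and rate ratio R = 0.78:

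SE = √(1/(nμ) + 1/(nμR)); power = Φ(|ln R|/SE − 1.96)

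- Power .90 at n = 100 requires μ ≈ 3.88.
- At n = 76: nμ ≈ 295, SE ≈ 0.0879, and 0.2485/0.0879 − 1.96 ≈ 0.87, so power is 0.807 (stated .81).
- With a design effect for the 1% ICC over 7 sites, μ ≈ 4.96 and power at 76 is 0.828.

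The tables agree with each other. The rate of about 3.9 is back-solved, not documented.

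**2. Planned absence.** Suppose a share s of each arm is away for 3 of 9 months with no capture at all. Mean observed time is 1 − s/3 in both arms, so the expected ratio is unchanged. Using μ = 3.92, which gives exactly .81 at 76 per arm, power becomes:

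| s | Power |
|---|---|
| 0% | 0.81 |
| 10% | 0.80 |
| 20% | 0.78 |
| 30% | 0.77 |

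**3. Differential loss with no offset.** Assumptions, because section L gives direction only:
- 15% of each arm is lost, forfeiting on average l = 1/2 to 2/3 of the window.
- A further e = 10 to 15% of coached patients is lost after month 6. They can forfeit at most 3/9 = 1/3, so take k = 1/6 to 1/3.
- Record review stops at loss, and partial counts are used unadjusted.

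Ratio under no true effect = (1 − 0.15l − ek)/(1 − 0.15l)

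| l | e | k | Ratio |
|---|---|---|---|
| 1/2 | 0.10 | 1/6 | 0.9083/0.925 = 0.982 |
| 1/2 | 0.15 | 1/3 | 0.875/0.925 = 0.946 |
| 2/3 | 0.10 | 1/6 | 0.8833/0.90 = 0.981 |
| 2/3 | 0.15 | 1/3 | 0.85/0.90 = 0.944 |

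The spurious reduction is about 2 to 6%. A true ratio of 0.78 would read as 0.78 × 0.944 = 0.74 to 0.78 × 0.982 = 0.77.

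**4. Balanced loss.** A simulation used 4,000 trials of 95 per arm, μ = 3.92, 20% loss in each arm, uniform exit times, no overdispersion and a simple Wald test. With no true effect the ratio was unbiased (1.00), but rejection was 7.6% without an offset and 4.9% with one. Varying observed time adds variance that a plain Poisson test ignores. A participant-level random effect might absorb part of this.

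**The case against.** **The SAP may treat incomplete patients as missing.** This has force. A reader might infer that time lost to death, absence or withdrawal is scored as free of exacerbations. No text says so, and the available-data, missing-at-random and multiple-imputation wording could mean that such patients have no outcome. But exacerbations come from charts, and a departed patient's chart still yields a number; nothing says it is set to missing. If it were, events already observed would be discarded. The imputation analyses are also tied to the primary analyses, and Table 1 lists exacerbations as secondary.

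**Missing a survey does not end record coverage.** Correct. The 9-month measures needed an in-person visit, whereas record review did not and is not described as limited to completers. If review ran to 9 months for everyone, the bias shrinks to that from deaths and departures from the county system. The plan does not say that it did.

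**Absence is partly captured and balanced.** Largely correct. It is planned before randomization, patients intend to stay with their clinic, and outside emergency visits and admissions are asked about. A patient who is away is still at risk, so this is a matter of ascertainment. The remaining gaps are outside prescriptions and months 6 to 9, for which section K describes no question about outside care.

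**A larger bias is tempting to claim.** Suppose 25 to 30% of coached and 15% of usual-care patients lose half to two-thirds of the window. The null ratio is then between (1 − 0.30 × 0.67)/(1 − 0.15 × 0.67) = 0.889 and (1 − 0.25 × 0.5)/(1 − 0.15 × 0.5) = 0.946, a spurious 5 to 11%. But the excess coached leavers would then go at about month 3 to 4.5 on average, and an imbalance should show at 6 months. Section L says completion was similar then.

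**Conclusion.** The gap is real and worth closing. The count model is stated without a time-at-risk term, and neither document says how a partly observed patient contributes to the 9-month count. If partial counts are used unadjusted, the rate ratio is biased by unequal observed time, probably in favour of coaching.

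The likely size is about 2 to 6%, against an expected effect of 20 to 26%: enough to matter near the significance boundary, not enough to create the expected effect. It rests on three assumptions: 15% common loss, a 10 to 15% coached-arm excess arising after month 6, and record review stopping at loss. It is smaller if review continued. The documents do not establish that lost time was scored as event-free, that the bias reaches 5 to 11%, or that the residence criterion biases the comparison.

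**What to change.** In the SAP:

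1. Add log(observed time) as an offset in the exacerbation model.
2. Define observed time as running from randomization to the earliest of 9 months, death, withdrawal of consent to record review, or documented departure from the county system. It must not depend on whether events or outside records occurred. Ending it at the last visit, or subtracting time away only when no outside records were obtained, would tie exposure to the outcome, because exacerbations generate visits and records.
3. State that record review continues to 9 months for participants who miss the 9-month survey.
4. Report deaths and observed time by arm beside the rate ratio. An offset corrects for length of observation; it does not make death or departure uninformative.

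The cost is SAP wording and slightly more abstraction, with dates largely from records already reviewed. The estimate becomes a rate rather than a raw count. The protocol reports follow-up in the past tense; if data collection has closed, the offset and the reporting by arm remain feasible from existing records.

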#### **F. Health coaching intervention**

Health coach training. The two study health coaches were college graduates without medical training or certification but who had previously worked with patients in the public health clinic system, one as a research assistant and the other as a volunteer health coach. Both received over 100 hours of training over 3 months using a COPD health coaching curriculum specific to the study. The curriculum was comprised of two primary domains: health coaching techniques and COPD-specific knowledge. The health coaching curriculum [CEPC website] focused on five areas: (1) active listening and non-judgmental communication, (2) helping patients create self-management goals and action plans, (3) healthcare navigation, (4) medication reconciliation and adherence and (5) closing the loop (checking for comprehension by asking patients to describe the key messages in their own words). COPD-specific training covered the physiology of COPD, related comorbidities, care recommended by the Global Initiative for Chronic Obstructive Lung Disease (GOLD), prevention and management of exacerbations, and lifestyle management. Upon completion of training, coaches were required to score at least 90% on three exams assessing content knowledge and to demonstrate mastery of coaching skills through simulated role-plays and observed health coaching sessions.

Health coaching activities. Patients received health coaching for 9 months. Each health coach worked with a total of 50 patients over the two-year duration of the study, with a maximum caseload of thirty patients at any given time. Patient needs and preferences guided the frequency of contact, with a suggested minimum frequency of connecting with the patient once every three weeks. Health coaches were expected to complete an initial visit within 2–3 weeks of enrollment, to meet in person with the patient at least 3 additional times over the course of the study and to have a phone check-in call at least every 3 weeks, including within two weeks after each medical visit. Coaches were also expected to conduct at least one in-depth consultation with the study pulmonary nurse practitioner specialist (PNPS) to optimize patient care and to attend at least one medical visit between the patient and their primary care provider

(PCP). Coaches provided patient education, worked with patients to set goals and develop action plans to reach those goals, facilitated patient access to clinical care and resources, and supported communication between patients, their PCP, and the PNPS.

As summarized below, coaches interacted with patients in one-on-one in person meetings, by telephone and during medical visits. Coaches also presented patients to the PNPS for consultation.

Initial meeting. The purpose of the initial meeting was to build rapport building and understand the patients' motivations, strengths, and barriers to self-management.

Subsequent meetings. Subsequent meetings occurred in person at the clinic or at the patient's home when possible, or by phone if an in-person meeting was not feasible. The purpose of these meetings, which generally lasting 15 to 90 minutes, was to set goals or address barriers to carrying out goals to assess patient knowledge, share information about target conditions, review inhaler use technique, and to assist with navigation of health and community resources (including making and keeping appointments, accessing classes and smoking cessation resources and meeting with a member of the behavioral health team). Home visits were utilized most frequently by patients that had difficulties with public transportation or general mobility. Home visits were also used to identify COPD/asthma triggers within the home, acquire accurate knowledge of what medications a patient has in the home, including any duplicate or expired medications, identify barriers to medication adherence, and ensure patients on oxygen have the necessary equipment.

Phone check-ins. Phone check-ins were done to provide on-going support for patient self-management, check for barriers to self-management and provide reminders for up-coming appointments.

Medical visits. Coaches also meet with patients at the time of their medical visits to conduct medication reconciliation, gather clinical information including administration of the COPD Assessment Tool, identify gaps in care and help patient to establish priorities and goals for the visit prior to the patient seeing the PCP. With the patient's permission, the health coach was present during the medical visit and could offer clarifications and support as needed. After the visit, the health coach reviewed the PCP's recommendations with patient to ensure patient understanding, and helped patients choose attainable goals and create an action plan for making changes to achieve those goals. The health coach called the patient approximately 2 weeks later to follow-up on action plans.

Consultations with the PNPS. The Health Coach consultation with the PNPS had several steps. Health coaches recorded patient medical history and co-morbidities, smoking history, risk and symptom assessment, COPD and asthma medications and treatment history, environmental triggers and screens for symptoms of sleep apnea, from review of the EMR and information supplied by the patient. The health coach then presented the patient's information to the PNPS who could gather additional information from the medial record if needed. The PNPS created a set of recommendations for changes in care using the GOLD guidelines, generally

without the need to see the patient. Recommendations could include changes to inhaler therapy, further diagnostic testing, and referrals to pulmonology, pulmonary rehabilitation, physical therapy, and other appropriate programs. Recommendations were communicated to the patient's PCP via the EMR and/or through secure email. The Health Coach followed-up with the patient to see if the recommendations had been accepted by the primary care provider and to provide education and support to the patient for implementing the recommendations.

### **G. Usual care control group**

Patients randomized to usual care continued to have visits with their primary care provider over the course of the 9-month period. They received any resources their provider and their clinic offer as part of standard care, including: access to COPD educators, respiratory therapists, COPD education classes, pulmonary rehabilitation, or smoking cessation classes.

### **H. Recruitment and enrollment**

Electronic billing records for the seven clinics and for the county hospital and ED were screened for patients with a COPD-related diagnosis (ICD-9 codes 491, 492, 496, 490+305.1, 493+305.1, 786+305.1) in the past year. Trained research assistants conducted chart reviews for patients identified by ICD-9 codes to gather clinical measures to determine eligibility criteria based on the previously stated criteria. Primary care providers received a list of their patients who appeared to be eligible after chart review and were asked to exclude those with severe physical or cognitive impairment, or who were known not to be otherwise eligible (e.g. deceased, no longer seen at clinic, or did not speak English or Spanish). The research associates then attempted to contact the remaining patients to confirm eligibility and, if eligible, to offer the chance to enroll in the study. Patients who did not have a COPD diagnosis confirmed by spirometry but who otherwise appeared to be eligible were offered spirometry. Eligible patients interested in enrolling in the study were scheduled to meet with a research assistant at their primary care clinic and were enrolled with informed consent. Baseline measurements, which included a survey, a 6 minute walk test and spirometry, were obtained prior to the patient being randomized.

